**Table 2: Last Known Alive Date for the Overall Survival** 

Source Data	Conditions
Last date patient known to be alive from Long- Term Follow-Up eCRF	Use if patient status is reported to be alive.  Do not use if patient status is not reported unknown
End of study	Not lost to follow up
Start/end dates from drug administration record	Non missing dose. Doses of 0 are allowed
Dosing prophylaxis eCRF	Prophylaxis given marked as yes.
End of treatment date from the End of Treatment eCRFs	No condition
Tumor assessment (RECIST v1.1 or iRECIST) date	Evaluation is marked as done
Laboratory/PK collection dates	Sample collection marked as done
Vital signs date	At least 1 non missing parameter value
Physical examination	Evaluation performed marked as yes
12-Lead ECG	Evaluation performed marked as yes
ECOG performance status date	Non missing ECOG performance status
Start/end dates of adverse events	Non missing verbatim term
Start/end dates of concomitant medications and procedures	Non missing verbatim term

## **B.** Primary Efficacy Analysis

The primary efficacy analysis will be the confirmed ORR as assessed by BICR per RECIST v1.1, and its 2-sided 95% confidence interval, calculated using Clopper-Pearson's method.

### Statistical Analysis Plan

Regeneron Pharmaceuticals Inc. / Protocol: CMP-001-010 IQVIA Biotech (Confidential) Project # RZA44091

Due to the Sponsor's decision to stop enrollment early, the sample size necessary to ensure a 95% level of confidence and a power of 90% will not be reached. Therefore, the test will be exploratory, and interpreted as such.

A table summarizing the number and percentage of subjects with a Best Overall Response (BOR) of CR, PR, SD, PD, or Not Evaluable will be presented. This table will also include the ORR and DCR, with their two-sided 95% CI calculated using the Clopper-Pearson method.

### C. Secondary Efficacy Analyses

Methodology for DOR, PFS, OS, iPFS, iDOR. Estimates of median with 95% CIs will be computed using the Kaplan-Meier method. Kaplan-Meier graphs will be visually displayed. Median Time-to-Event will be estimated at the 50th percentile of the corresponding Kaplan-Meier estimates. The event-free rate with the two-sided 95% CIs using Greenwood's formula will be calculated for 3-month interval timepoints (e.g., 6, 9, 12 and 18 months). The reasons for censoring will be summarized categorically with the number and percentage of subjects tabulated.

*DOR by BICR.* A table summarizing the secondary endpoint of DOR by BICR will be produced for subjects with a confirmed BOR of CR or PR only, following the methodology presented above.

PFS by BICR. The secondary endpoint of PFS by BICR will be summarized following the methodology presented above.

Treatment Effect in Non-injected Target Lesions. The confirmed ORR in non-injected target lesions per RECIST v1.1 assessed by BICR measurements will be evaluated using the same approach as the primary efficacy analysis ORR.

Efficacy Assessments per RECIST v1.1 by Investigator. Analysis of ORR, BOR, DCR, DOR, and PFS based on RECIST v1.1 by Investigator assessment will be performed using the same methods described in the previous sections.

OS. The secondary endpoint of OS will be summarized following the methodology presented above.

*iORR*, *iDOR*, *iPFS*. Post-progression disease assessments of tumor response based on iRECIST by Investigator assessment will also be summarized. Analysis of immune objective response rate (iORR), immune duration of response (iDOR), and immune progression-free survival (iPFS) based on iRECIST by Investigator assessment will be performed using the same methods described in the previous sections.

Regeneron Pharmaceuticals Inc. / Protocol: CMP-001-010 IQVIA Biotech (Confidential) Project # RZA44091

The following efficacy figures will be generated using the confirmed BICR RECIST v1.1 BORs for subject level classification for the ITT Analysis set. Additional figures for the Investigator assessment and iRECIST assessments may be produced.

- A waterfall plot will be generated summarizing the best percent change in tumor burden of injected and non-injected target lesions from the Screening/Baseline target lesion assessment for each subject, for responders only:
  - Tumor burden as reflected by the sum of the diameters (SOD) of all target lesions, concerning longest diameters for extranodal lesions and short axis for lymph nodes, will be assessed at baseline and at each disease assessment after the first dose of CMP-001.
  - Tumor burden change will be calculated as the percentage change in SOD of target lesions from baseline for each efficacy evaluable subject at each disease assessment.
  - o Each BOR category will be displayed in different colors.
- A Spider plot of the percent changes in tumor burden for target lesion measurements (including the sum of the diameters (SOD) of all target lesions, the longest diameters for extranodal lesions, and the short axis for lymph nodes) from the Screening/Baseline target lesion assessment over time.
  - o Each BOR category will be displayed in different colors
- A Swimmer plot delineating the occurrence of the clinical outcomes of interest over time, including the following information:
  - Duration of study treatment
  - Treatment ongoing
  - Time to BOR based on RECIST v1.1 as assessed by BICR, except that PD will be the first occurrence of PD. The swimmer plot will display each Confirmed BOR category as a separate color.
  - o Time to death
- Kaplan-Meier plots displaying time-to-event on DOR, PFS, OS, per RECIST v1.1 as assessed by BICR, and by Investigator:
  - Estimate of median and the corresponding two-sided 95% CIs for median

CONFIDENTIAL

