All other lesions (or sites of disease) including pathological lymph nodes should be identified as non-target lesions and should also be recorded at Baseline. Measurements are not required, and these lesions should be followed as 'present,' 'absent,' or in rare cases 'unequivocal progression.' In addition, it is possible to record multiple non-target lesions involving the same organ as a single item on the case record form (ie, 'multiple enlarged pelvic lymph nodes' or 'multiple liver metastases').

Tumor Response Criteria

Evaluation of Target Lesions

Complete response: Disappearance of all target lesions. Any pathological lymph nodes (whether target or non-target) must have reduction in short axis to < 1 cm.

Partial response: At least a 30% decrease in the sum of diameters of target lesions, taking as reference the Baseline sum diameters.

Progressive disease: At least a 20% increase in the sum of diameters of target lesions, taking as reference the smallest sum on study (this includes the Baseline sum if that is the smallest on study). In addition to the relative increase of 20%, the sum must also demonstrate an absolute increase of at least 0.5 cm (NOTE: the appearance of 1 or more new lesions is also considered progression).

Stable disease: Neither sufficient shrinkage to qualify for PR nor sufficient increase to qualify for PD, taking as reference the smallest sum diameters while on study.

Evaluation of Non-Target Lesions

Complete response: Disappearance of all non-target lesions and normalization of tumor marker level. All lymph nodes must be non-pathological in size (< 1 cm short axis).

Non-complete response/Non-progressive disease: Persistence of 1 or more non-target lesion(s) and/or maintenance of tumor marker level above the normal limits.

Progressive disease: Unequivocal progression of existing non-target lesions (NOTE: the appearance of 1 or more new lesions is also considered progression).

Evaluation of Best Overall Response

The best overall response (BOR) is recorded from the start of the study treatment until the End of Clinical Trial, taking into account any requirement for confirmation. The subject's BOR assignment will depend on the findings of both target and non-target disease and will also take into consideration the appearance of new lesions. In non-randomized studies where response is the primary endpoint, confirmation of PR or CR is needed to deem either one the 'BOR.'

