### A. Efficacy Endpoints

Confirmed Objective Response Rate (ORR)

The confirmed ORR is defined as the proportion of subjects in the analysis set who have confirmed best response as CR or PR per RECIST v1.1 as assessed by BICR.

The confirmed ORR will be calculated as the number of subjects with a confirmed CR or PR divided by the number of subjects in the analysis population [ORR = (confirmed CR + confirmed PR)/number of subjects] for the ITT Analysis Set. 95% Clopper-Pearson CIs for the ORR will be calculated.

Subjects who discontinue due to death as a result of disease progression, or disease progression, prior to having a post-Baseline tumor assessment will be classified as having a best response of PD. Subjects who discontinue prior to having a post-Baseline scan for other reasons will be counted as non-responders in the ITT analyses. Objective Response assessment evaluated after new anti-cancer treatment will not be considered for BOR calculation.

Confirmed Best Overall Response (BOR)

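### The first waterfall plot in SAP VIII.C is limited to responders, which contradicts its own specification and selects on the shrinkage it displays

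*SAP*

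**What the plan says.** SAP VIII.C (Secondary Efficacy Analyses) introduces the efficacy figures as being produced "using the confirmed BICR RECIST v1.1 BORs for subject level classification for the ITT Analysis set". The first figure listed is a waterfall plot of best percent change in tumor burden, measured "from the Screening/Baseline target lesion assessment for each subject, for responders only".

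The sub-bullets of that same plot define tumor burden as the sum of diameters over all target lesions. They calculate the "percentage change in SOD of target lesions from baseline for each efficacy evaluable subject at each disease assessment" and add that "Each BOR category will be displayed in different colors".

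SAP VIII.A defines the ORR as the "proportion of subjects in the analysis set who have confirmed best response as CR or PR per RECIST v1.1 as assessed by BICR", which fixes who a responder is. Protocol Appendix D requires, for a target-lesion PR, "At least a 30% decrease in the sum of diameters of target lesions" relative to baseline.

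SAP VI.J defines five analysis sets: Intent-to-Treat, Safety, Per Protocol, Pharmacodynamic and Immunogenicity. An efficacy evaluable set is not among them.

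**The concern.** A waterfall plot is normally read as the distribution of tumor change across the treated population: how many subjects shrank, how many were flat and how many grew. Limiting it to responders removes the flat and growing subjects by definition, so the figure mostly restates the response criterion.

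The specification also cannot be followed as a whole. It names three populations for one plot (ITT, efficacy evaluable, responders) and does not say which governs. Two programmers could produce materially different figures from the same text.

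The SAP makes all analyses descriptive and exploratory after enrollment stopped early, and there is no control arm. Displays therefore carry more of the interpretation than usual, and a plot that shows only large reductions is easy to over-read.

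**Working it through.** **Inputs**
- ITT size: 44 subjects treated (SAP II.C; ITT definition in SAP VI.J.1).
- Planning ORR 20%, null ORR 7% (Protocol 9.1).
- ORRs in the earlier study of CMP-001 with pembrolizumab: 23.5% (23/98) by RECIST v1.1, and 27.6% (27/98) when responses after initial progression are included (Protocol 1.2.1).
- Early discontinuation rate 15% (Protocol 9.1).
- First on-study disease assessment at Week 13 (SAP II.A).
- Observed ORR: not given in either document.

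**Step 1. The plan's own figure.** The documents give no figure for the share of subjects plotted. The number borrowed here is the 20% planning ORR, and the calculation it comes from reproduces. With 69 subjects and an exact binomial test at 0.025 per tail against 7%, rejection needs at least 10 responses, with upper-tail error 0.0215 and power 0.907 at 20%. With 68 subjects the power is 0.897. The Clopper-Pearson interval for 20/100 is 12.7% to 29.2%, as stated.

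**Step 2. Populations side by side.**

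| Place in SAP VIII.C | Who is plotted |
|---|---|
| Sentence introducing the figures | ITT set |
| Waterfall parent bullet | Responders |
| Waterfall sub-bullet on change | Efficacy evaluable subjects (undefined) |
| Waterfall sub-bullet on colour | Every BOR category |

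Under the parent bullet only the CR and PR categories can have bars.

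**Step 3. Where the bars can lie.** A target-lesion PR requires a fall of at least 30% in the sum. A target-lesion CR requires non-nodal lesions to disappear and nodes to fall below 1 cm. Appendix D treats nodes under 1.5 cm in short axis as non-measurable, so a target node starts at 1.5 cm or more and falls by more than (1.5 - 1.0)/1.5 = 33%. The best change cannot be less favorable than the change at the response visit. So if each bar is the central reviewers' sum over all target lesions, every responder's bar is at or below -30%.

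**Step 4. Share left off.** Expected responders = ORR x 44; share left off = 1 - ORR.

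| Assumed ORR | Responders plotted | Left off | Share left off |
|---|---|---|---|
| 7% | 3.1 | 40.9 | 93% |
| 20% | 8.8 | 35.2 | 80% |
| 23.5% | 10.3 | 33.7 | 76.5% |
| 27.6% | 12.1 | 31.9 | 72% |

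If the true ORR were 20%, the central 95% binomial range is 4 to 14 responders out of 44, that is 91% to 68% left off.

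**Step 5. How much is due to the restriction itself.** Subjects without a post-baseline scan cannot be plotted under any rule. Their number is not in the documents. As an illustration only, take the 15% early discontinuation rate as a stand-in: 0.15 x 44 = 6.6 subjects. The restriction then removes 44 - 6.6 - 8.8 = 28.6 subjects, or 65% of the ITT set.

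**The case against.** **Other displays cover non-responders.** A reader might infer that the SAP conceals tumor change in non-responders, or that this plot is its main display of depth of response. The documents support neither. The SAP does not rank its figures; this is simply the first listed. Under the same section the spider plot and the second waterfall plot (injected against non-injected lesions) state no responder restriction. The BOR table in SAP VIII.B counts every category, and all lesion assessments are listed. This objection stands and confines the point to one figure. It does not repair that figure: the BOR table shows no depth, the spider plot shows trajectories, and the second waterfall splits lesions by injection status.

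**Four in five is not a known figure.** It is an expectation at a planning ORR, and part of it would remain after the fix (Step 5). This stands, so the share is given as an assumption with a range.

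**The -30% bound is conditional.** The lead-in uses central-review BOR to classify subjects but does not say whose measurements are plotted. With Investigator measurements, a responder by central review could lie above -30%. If injected and non-injected lesions were drawn as separate bars, one subset need not shrink by 30%. The sub-bullet's use of all target lesions favors the single-sum reading, but the bound needs its condition stated.

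**The colour conflict is mild.** CR and PR are two categories, and the same line recurs under the spider plot, so colouring by BOR still works with responders only. The stronger conflict is over the population.

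**The stakes are limited.** The figure is descriptive, the analyses are labelled exploratory, and Protocol 9.5 calls for no waterfall plot. This stands too.

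**Conclusion.** The point holds for this one figure. As written, the first waterfall plot contradicts its ITT lead-in and its own sub-bullet on who is measured, and it selects subjects on the tumor shrinkage it then displays. Following the text produces a misleading plot, which is worse than a missing detail.

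Assuming an ORR of 20%, about 9 of 44 ITT subjects would appear and about 35 (80%) would not, with a range of 72% to 93% for ORRs of 27.6% down to 7%. An unknown part of that share lacks a post-baseline scan and would be absent in any case. That every bar lies at or below -30% holds only if central-review sums of all target lesions are plotted.

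The confirmed ORR, its Clopper-Pearson interval and every other planned table and listing are unaffected. This is a correction worth making before the figure is programmed, but it is not a threat to the primary result.

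**What to change.** In the waterfall bullet of SAP VIII.C:
- Delete the final three words of "from the Screening/Baseline target lesion assessment for each subject, for responders only".
- Plot every ITT subject with a baseline and at least one post-baseline target-lesion sum, coloured by confirmed BOR from central review.
- State that the plotted measurements are those of the central review.
- Replace the undefined efficacy evaluable population in the sub-bullet with the definition above.
- Footnote the number of ITT subjects not plotted and the reasons.

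A responder-only version could be kept as a supplement if labelled as such. The cost is a few words in the SAP, one filter in the figure program and one footnote. No new data are needed.

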### Statistical Analysis Plan

Regeneron Pharmaceuticals Inc. / Protocol: CMP-001-010 IOVIA Biotech (Confidential) Project # RZA44091

- o Event-free rates at selected timepoints
- A Forest plot suggesting ORR and the associated two-sided 95% CI
- For the analysis of the potential difference in tumor shrinkage in injected and non-injected target lesions within the same subject, a waterfall plot delineating the maximal percentage reduction in SOD from baseline for injected and non-injected target lesions, respectively, will be provided.

Listings of efficacy-related data (by BICR or by Investigator) will include the following:

- All lesion assessments (target lesion, non-target lesion, new lesion).
- Response assessments.
- Time to events (DOR, PFS, OS)

### D. Efficacy Analysis on Subgroups of Subjects

The below subgroup analysis (not limited to) for efficacy will be explored using forest plots of the calculated ORRs with their 95% CIs.

- Serum LDH at diagnosis (Elevated, Normal)
- BRAF mutation (Yes, No)
- Number of Lines of Prior Therapies  $(1, 2, \ge 3)$ . Note the categories can be modified based on the data).
- Best Response to Prior Anti-PD-L1 (CR, PR, SD, PD, NE, NA, Unknown)
- Clinical Disease Stage at diagnosis (M0/M1a/M1b, M1c/M1d)

### E. Exploratory Efficacy Analysis

The performance of the statistical analysis for the exploratory efficacy endpoint is contingent on the availability of the data source. Given the response assessment based on itRECIST by Investigator has not been collected, and that the RECIST v1.1 and iRECIST were deemed sufficient for the purpose of the response assessment in the study from the Medical's perspective, no exploratory efficacy analyses will be carried out for the exploratory phase 2 study.

Regeneron Pharmaceuticals Inc. / Protocol: CMP-001-010 IQVIA Biotech (Confidential) Project # RZA44091

### IX. Safety Analyses

Safety analyses will use data from the Safety Analysis Set. Subjects will be analyzed according to the actual study treatment received (i.e., the actual treatment arm variable(s) in SDTM/ADaM).

### A. Exposure

Exposure to CMP-001 and Nivolumab will be summarized separately with descriptive statistics for the number of doses received, the duration of treatment to each drug (weeks), the planned dose intensity, the actual dose intensity, and the relative dose intensity (%).

### 1. Duration of Treatment

Duration of Treatment (DoT) of CMP-001 and Nivolumab will be summarized in a descriptive manner, respectively. DoT will be calculated as follows:

DoT (weeks) = [min(last dose date + 21 days, discontinuation/completion date) – first dose date] / 7

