5. TREATMENT OF SUBJECTS

5.1. Administration of Study Treatment

5.1.1. Nivolumab

Subjects will receive CMP-001 10 mg IT injection followed by nivolumab 360 mg IV at W1D1 and Q3W thereafter until the subject satisfies a condition for study treatment discontinuation. Nivolumab should be administered to the subject according to the nivolumab Investigator's Brochure. Nivolumab should be administered until the subject satisfies a condition for study treatment discontinuation (Section 4.5.). On visits where both study treatments are administered, nivolumab should be administered after CMP-001. There is no specified waiting period between the end of CMP-001 injection and the initiation of nivolumab infusion.

Participants should receive nivolumab at a dose of 360 mg as a 30-minute infusion each treatment cycle until progression, unacceptable toxicity, withdrawal of consent, or the study ends, whichever occurs first.

There will be no dose escalations or reductions of nivolumab allowed. Participants should be dosed in accordance with the Schedule of Assessments (Table 1).

Participants should be carefully monitored for infusion reactions during nivolumab administration. If an acute infusion reaction is noted, participants should be managed according to Section 5.1.5.

Doses of study treatment(s) may be interrupted, delayed, or discontinued depending on how well the participant tolerates the treatment. Dosing visits are not skipped, only delayed.

The assessment for discontinuation of nivolumab should be made separately from the assessment made for discontinuation of CMP-001. If discontinuation criteria are met for CMP-001 but not for nivolumab, treatment with nivolumab may continue if CMP-001 is discontinued.

Please refer to the current nivolumab Investigator's Brochure and/or Pharmacy Manual for further details regarding storage, preparation, and administration of nivolumab.

Care must be taken to assure sterility of the prepared solution as the product does not contain any antimicrobial preservative or bacteriostatic agent.

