# **EIQVIA**BIOTECH

### Statistical Analysis Plan

Regeneron Pharmaceuticals Inc. / Protocol: CMP-001-010 IQVIA Biotech (Confidential) Project # RZA44091

• After imputation, the imputed date will be compared against the date of death, if available. If the planned imputed date is later than the date of death, the date of death will be used as the imputed date instead. If there is no date of death in the EDC for a subject and the planned imputed date is later than the End-of-Treatment (the last drug received) date + 100 days, then the End-of-Treatment (the last drug received) date + 100 days will be used for the stop date.

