## 2. Dosing Intensities

- (1) Actual dose intensity (mg/week) will be calculated as the total actual cumulative dose received divided by duration of treatment (weeks) for CMP-001 and Nivolumab, respectively.
- (2) Planned dose intensity (mg/week) will be calculated as the total planned cumulative dose to be received divided by the Planned Duration of Treatment (weeks) based on the protocol schedule.

Planned Duration of Treatment (weeks) = number of planned treatments \* 3 (weeks)

(3) Relative dose intensity (%) will be calculated based on the actual cumulative dose received relative to the planned cumulative dose throughout the duration of treatment as follows:

Relative dose intensity (%) = (actual dose intensity / planned dose intensity) \* 100%

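### Cutting treatment duration at the discontinuation date inflates nivolumab relative dose intensity for subjects who stop fewer than 21 days after their last dose

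*SAP*

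**What the plan says.** SAP IX.A.1 gives one formula for both drugs: "DoT (weeks) = [min(last dose date + 21 days, discontinuation/completion date) – first dose date] / 7". No day is added at the end, unlike the SAP's formulas for time on study, DOR, PFS and OS, which all add 1.

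SAP IX.A.2 then builds three quantities.

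- Actual intensity: "Actual dose intensity (mg/week) will be calculated as the total actual cumulative dose received divided by duration of treatment (weeks".
- Planned intensity: "total planned cumulative dose to be received divided by the Planned Duration of Treatment (weeks) based on the protocol schedule". The planned duration is "Planned Duration of Treatment (weeks) = number of planned treatments", multiplied by 3 weeks.
- Relative dose intensity, as displayed: "Relative dose intensity (%) = (actual dose intensity / planned dose intensity", times 100%. The sentence that introduces this formula describes it as "based on the actual cumulative dose received relative to the planned cumulative dose throughout the duration of treatment".

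The nivolumab schedule is "nivolumab 360 mg IV at W1D1 and Q3W thereafter" (Protocol 5.1.1). The same section rules out dose escalation and reduction, and says that dosing visits are delayed rather than skipped.

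The SAP does not define the discontinuation/completion date for each drug. It has no rule for a duration of zero and no cap on relative dose intensity. Protocol 9.4 calls for dose intensity and relative dose intensity to be summarized, and SAP VI.G includes drug exposure in the ad-hoc analysis.

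**The concern.** The two sides of the ratio follow different conventions. The planned denominator gives the last dose its whole 3-week interval. The actual denominator removes whatever part of that interval falls after discontinuation, while the numerator keeps the whole last dose.

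Relative dose intensity is there to show under-delivery. Under these formulas the subjects who stop earliest after a dose, and after the fewest doses, get the largest upward distortion, and real delays in such subjects are partly cancelled. Since nivolumab cannot be escalated, a value above 100% from full doses given on schedule is an artifact. A reader of the exposure table could not tell it from real over-delivery.

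**Working it through.** The documents state no duration or intensity value, so there is no figure to reproduce. The SAP formulas are applied directly.

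**Inputs**

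- Dose 360 mg every 3 weeks (Protocol 5.1.1).
- k = number of full doses given.
- D = cumulative delay in days, so the last dose falls 21(k − 1) + D days after the first.
- d = days from last dose to discontinuation, with d ≤ 21.
- Assumption: the date in SAP IX.A.1 is the treatment discontinuation date for nivolumab.

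**Formulas**

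- Planned intensity for n planned doses = 360n/(3n) = 120 mg/week, whatever n is.
- Duration of treatment = [21(k − 1) + D + d]/7 weeks.
- Relative dose intensity = [360k/duration]/120 = 21k/[21(k − 1) + D + d].

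The ratio exceeds 100% when 21k > 21(k − 1) + D + d, that is, when D + d < 21. The denominator is zero only for k = 1 and d = 0.

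**Full doses on schedule (D = 0)**

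| Doses | d = 0 | d = 7 | d = 14 | d = 20 | d = 21 |
|---|---|---|---|---|---|
| 1 | undefined | 300% | 150% | 105% | 100% |
| 2 | 200% | 150% | 120% | 102.4% | 100% |
| 4 | 133.3% | 120% | 109.1% | 101.2% | 100% |
| 8 | 114.3% | 109.1% | 104.3% | 100.6% | 100% |
| 35 | 102.9% | 101.9% | 101.0% | 100.1% | 100% |

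For example, four doses with a stop at 14 days give 84/(63 + 14) = 109.1%. If the last dose keeps its 21 days, every row gives 100%.

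**With delay**

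| Doses | D | d | SAP formula | Last dose keeps 21 days |
|---|---|---|---|---|
| 4 | 14 | 7 | 84/84 = 100.0% | 84/98 = 85.7% |
| 4 | 14 | 10 | 84/87 = 96.6% | 84/98 = 85.7% |
| 4 | 21 | 7 | 84/91 = 92.3% | 84/105 = 80.0% |
| 5 | 21 | 14 | 105/119 = 88.2% | 105/126 = 83.3% |

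None of these exceeds 100%, yet all are too high.

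**How ordinary the situation is.** The first scheduled scan is due at W13D1 with a window of 7 days before (Protocol Table 1, footnote u). That follows four on-schedule doses, the last at W10D1, by 14 to 21 days. A stop dated at that scan gives 109.1% down to 100%.

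**Effect on the mean.** With the 44 enrolled subjects (SAP II.C), one subject shown at 300% instead of 100% raises the mean by (300 − 100)/44 = 4.5 points. One shown at 109.1% raises it by 9.1/44 = 0.2 points.

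**The case against.** Several points can be made for the plan.

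- *The cut looks deliberate.* Ending exposure at discontinuation is a sensible description of time on treatment, and adding 21 days after every last dose counts time after death or a change of therapy. This stands as a cost of the fix. It does not justify dividing by the cut duration when the planned side is not cut.
- *The date is undefined.* If it means study discontinuation, the cut would seldom apply. This stands as a condition on the finding. The formula concerns treatment duration by drug, so the treatment date is the natural reading. The nearest protocol definition, written for CMP-001 in Table 1 footnote a, is the time of the Investigator's decision, which can fall anywhere within the 21 days.
- *The introductory sentence can be read as a ratio of cumulative doses.* On that reading four scheduled and four given doses are 1440/1440 mg = 100%, while the displayed formula gives 120% for a stop at 7 days. The ambiguity is real. The displayed formula is the likelier one to be programmed, and the SAP should say which governs.
- *The consequences are small.* All analyses are descriptive and exploratory, and no test or efficacy endpoint uses this quantity. Medians accompany means (SAP VI.L), and dose delays are tabulated and each dose listed (SAP IX.A.3). This stands and limits the weight of the point.

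Two stronger readings are tempting, and the documents support neither. A reader might infer that anyone who stops within 21 days of the last dose exceeds 100%. The delay table shows otherwise, a stop exactly on day 21 gives 100%, and a partial infusion also lowers the value: four on-schedule doses with half of the last one given and a stop at 14 days give (3.5 × 21)/77 = 95.5%. A reader might also infer that the whole last interval is always lost, because SAP VI.C glosses end of treatment as "End-of-Treatment (the last drug received) date + 100 days". That phrase belongs to a rule for imputing stop dates of adverse events and medications. It does not define the date in SAP IX.A.1, and it shows only the worst case, d = 0.

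**Conclusion.** The defect is real but modest. As displayed, the formulas inflate nivolumab relative dose intensity whenever a subject stops fewer than 21 days after the last dose. They push it above 100% for full doses only if delay plus gap is under 21 days, and leave it undefined for one dose with a same-day stop. Adding the 1 day used elsewhere in the SAP would not cure that last case: the duration would be 1/7 week and the result 360/(1/7)/120 = 2100%.

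For a stop prompted by the first scheduled scan after four on-schedule doses the excess is at most about 9 points. The very large values need a stop soon after one or two doses, and the documents give no count of such subjects.

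The conclusion rests on two assumptions: that the date is the treatment discontinuation date for the drug, and that the displayed ratio governs over the sentence that introduces it. The reach is the descriptive exposure summary in 44 subjects; the primary endpoint is untouched. CMP-001 has its own mismatch, a 3-week multiplier against seven weekly doses, which is a separate correction.

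**What to change.** In SAP IX.A, for nivolumab actual and relative dose intensity, use (last dose date + 21 days − first dose date)/7 as the denominator, without the cut. Full on-schedule courses then give 100% for any number of doses, a single dose gives 3 weeks and is always defined, and a value above 100% would mean doses given ahead of schedule.

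Keep the truncated duration as descriptive time on treatment only. Define the discontinuation/completion date separately for each drug. State that the displayed ratio governs over the cumulative-dose wording that introduces it.

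The cost is a few sentences in the SAP and a one-line program change for the denominator, with no new data. The trade-off is that the intensity denominator can extend past death or the start of another therapy, which a table footnote should say. The CMP-001 planned duration should be corrected separately, since changing the actual denominator alone would not give a valid ratio there.
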